### **1.17 Variables related to lipid profile**

- Derivation: Total and HDL cholesterol and triglycerides will be measured by the Pathology Department in Hammersmith Hospital (Imperial College Healthcare NHS Trust). LDL- cholesterol will be computed using the Friedwald relation:

$$LDL\ cholesterol = Total\ cholesterol - HDL\ cholesterol + \frac{triglyceride}{2.2}$$

- Analysis: modified ANCOVA and LMM; no additional analysis.

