6 STUDY PROCEDURES AND SCHEDULE

6.1 STUDY PROCEDURES/EVALUATIONS

6.1.1 STUDY SPECIFIC PROCEDURES

The following list of procedures will be performed on all participants:

- Medical history - Participants will be asked a series of questions by the research nurse to ensure that they do not meet any of the exclusion criteria of the study.
- Genetic testing – saliva samples will be provided.
- Physical examination – Assessment of weight, height, waist circumference, blood pressure, lean mass, fat mass.
- Hematology – blood test to examine total cholesterol, HDL cholesterol, LDL cholesterol, fasting triglycerides, HbA1c
- Biological specimen collection – saliva samples will be obtained via the collection of 2ml of spit per sample. Another saliva sample will be provided by means of a buccal cheek swab, to be used in conjunction with the NudgeBox.
- Insulin sensitivity – 0 minutes on 75g glucose OGTT, 120 minutes on 75g glucose OGTT, 120 minutes c-peptide following 75g glucose OGTT, HOMA insulin sensitivity and secretion measurement
- Pregnancy test
- Food frequency questionnaire
- Trial commencement and completion questionnaires

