## Definitions

Impaired glucose regulation: impaired fasting glucose (IFG) or impaired glucose tolerance (IGT).

Impaired fasting glucose:

$6.1\text{ mmol/L} \leq \text{Fasting plasma glucose (FPG)} \leq 6.9\text{ mmol/L}$  AND  $2\text{ hr plasma glucose: } < 7.8\text{ mmol/L}$

Impaired glucose tolerance:

- $\text{FPG} \geq 7\text{ mmol/L}$  AND  $7.8\text{ mmol/L} \leq \text{2-hour plasma glucose} < 11\text{ mmol/L}$  after glucose load
- HbA1c between 42 and 47 mmol/mol (6.0–6.4%)

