## 1.5 Secondary endpoints

Secondary outcomes include differences at weeks 6, 12 and 26 between arms in the cross sectional values and changes from baseline of the variables listed below.

- Variables related to glucose regulation:
  - FPG at other time points
  - Plasma glucose at 120 minutes (P120) following 75g OGTT
  - Insulin resistance index (IRI) computed using the Homeostasis model assessment (HOMA) of beta cell function
  - c-peptide at 120 minutes following 75g OGTT
  - HbA1c
- Variables related to anthropometric measurements
  - Body weight
  - Body Mass Index (BMI)
  - Lean mass
  - Fat mass
  - Waist circumference
- Variables related to lipid profile
  - Total cholesterol
  - Fasting triglycerides
  - Low-density lipoprotein (LDL) cholesterol
  - High-density lipoprotein (HDL) cholesterol
- Variables related to clinical markers
  - Systolic Blood pressure (SBP)
  - Diastolic blood pressure (DBP)
- Dietary intake
  - Total energy intake
  - Carbohydrate intake
  - Fat intake
  - Saturated fat intake
  - Salt intake

- Vitamin D
- Vitamin B6
- Vitamin B12

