### **1.8 Baseline characteristics and description of the study population**

Table 1 below lists the baseline variables of interest and presents the methods of derivation. The baseline variables will be summarised for each treatment arm using the mean with standard deviation (sd) for continuous data and count (n) with proportion (%) for categorical data. Statistical testing of between group imbalance in the baseline covariates will not be performed unless required for regulatory or publication reasons. A tabular presentation will be used to display the results.

Table 1. Baseline variables

Description	Definition	Type	Unit	Coding /derivation	CRF
Age		Num	Year	Number of years from date of birth (months : year)	Anonymised Randomisation log
Sex			N (%)		Screening enrolment log
HbA1c		Num	Mmol/mol		Visit2-CRF
Randomisation group	Intervention group assigned at randomization			Anonymised Randomisation log	
Height		m		Visit3-CRF	
Weight		Kg		Visit3-CRF	
Body mass index (BMI)		Kg/m 		Visit3-CRF	
BMI>30		N (%)		Visit3-CRF	
Fat body mass		Kg		Visit3-CRF	
Lean body mass		Kg		Visit3-CRF	
Waist circumference		cm		Visit3-CRF	
Systolic BP		mmHg		Visit3-CRF	
Diastolic BP		mmHg		Visit3-CRF	

Pulse		bpm		Visit3-CRF
Glucose t0	Plasma glucose at time 0 after 75g glucose load	Num	mM/L	Visit3-CRF
Glucose t120	Plasma glucose at 120' after 75g glucose load	Num	mM/L	Visit3-CRF
Insulin t120	Plasma Insulin at 120' after 75g glucose load		IU/L	Visit3-CRF
C-peptide t0	C-peptide at t0 after 75g glucose load		mM/L	Visit3-CRF
Total cholesterol			mM/L	Visit3-CRF
HDL-cholesterol			mM/L	Visit3-CRF
Non-HDL cholesterol			mM/L	Visit3-CRF
LDL cholesterol			mM/L	Visit3-CRF
Fasting TG			mM/L	Visit3-CRF

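### SAP 1.17 adds the triglyceride term when it derives LDL cholesterol, which overstates a listed secondary endpoint by 0.909 × TG; as a lesser point, the SAP's glucose rule for IGT contradicts protocol 3.3

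*SAP*

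**What the plan says.** **LDL.** SAP 1.17 names the measured quantities: "Total and HDL cholesterol and triglycerides will be measured by the Pathology Department in Hammersmith Hospital". It then says that LDL "cholesterol will be computed using the Friedwald relation" and prints "LDL\ cholesterol = Total\ cholesterol - HDL\ cholesterol + \frac{triglyceride}{2.2". In plain notation this is LDL = TC − HDL + TG/2.2. Neither document gives another LDL formula.

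LDL is a named secondary endpoint. SAP 1.5 states "Secondary outcomes include differences at weeks 6, 12 and 26 between arms", and its list includes "Low-density lipoprotein (LDL) cholesterol". Under SAP 1.17 it is analysed by modified ANCOVA and a linear mixed model.

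Two other places bear on where the LDL value comes from. Protocol 6.1.1 describes a "blood test to examine total cholesterol, HDL cholesterol, LDL cholesterol, fasting triglycerides, HbA1c". The baseline table in SAP 1.8 gives the Visit 3 CRF as the source of LDL. The same table lists "Non-HDL cholesterol" as a separate variable.

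**IGT.** The first bullet under impaired glucose tolerance in the SAP Definitions combines fasting plasma glucose of 7 mmol/L or more with a 2-hour value from 7.8 to below 11 mmol/L. Protocol 3.3 uses the same 2-hour limits with fasting glucose below 7 mmol/L. A second SAP bullet reads "HbA1c between 42 and 47 mmol/mol", with no and/or between the two.

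**The concern.** Non-HDL cholesterol is TC − HDL, and LDL is one part of it. The printed rule sets LDL equal to non-HDL cholesterol plus a positive amount, which no participant's data can satisfy. Anyone programming the SAP as written would produce impossible values for a prespecified endpoint.

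The error is not a constant that drops out of a between-arm comparison. It is proportional to TG, which is itself a secondary endpoint and could respond to diet. If one arm lowers TG and leaves LDL alone, the rule reports a lower LDL in that arm. One effect would then appear under two endpoints, in a plan that makes no multiplicity adjustment (SAP 1.20). The SAP Background assumes that the DNA-based diet improves the lipid profile, so the distortion runs in the direction of the hypothesis.

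The IGT mismatch matters less. SAP 1.6 excludes from the per-protocol population participants without impaired glucose regulation and refers back to the SAP definition. Protocol 9.4 plans a logistic regression of the proportion with IGR, without a time point; it is affected only if it uses the SAP definition.

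**Working it through.** The plan states no LDL figure to reproduce, so the check is algebra followed by an illustration.

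**Inputs from the documents:** the printed rule and its divisor of 2.2 (SAP 1.17); one unit, mM/L, read as mmol/L, for all lipids (SAP 1.8 baseline table); non-HDL cholesterol as a separate variable (same table).

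**Assumed inputs:** TC 5.0 and HDL 1.3 mmol/L; TG 0.8, 1.7 and 3.0 mmol/L; between-arm TG differences of 0.1, 0.3 and 0.5 mmol/L. The documents give no lipid values.

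**Step 1, internal bound.** Printed LDL − non-HDL = (TC − HDL + TG/2.2) − (TC − HDL) = TG/2.2 = 0.455 × TG. This is positive for any TG above zero. LDL cannot exceed non-HDL cholesterol, so the printed value is too high by at least this amount, whatever the correct formula is.

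**Step 2, excess over the minus-sign value.** (TC − HDL + TG/2.2) − (TC − HDL − TG/2.2) = 2 × TG/2.2 = 0.909 × TG. With the SAP's own term and divisor, subtraction is the only sign that puts LDL below non-HDL cholesterol.

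**Step 3, illustration.** Non-HDL = 5.0 − 1.3 = 3.70 mmol/L.

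| TG | TG/2.2 | LDL as printed | LDL with minus | Excess | HDL + printed LDL (TC is 5.0) |
|---|---|---|---|---|---|
| 0.8 | 0.36 | 4.06 | 3.34 | 0.73 | 5.36 |
| 1.7 | 0.77 | 4.47 | 2.93 | 1.55 | 5.77 |
| 3.0 | 1.36 | 5.06 | 2.34 | 2.73 | 6.36 |

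As TG rises, the printed LDL goes up where the minus-sign value goes down. In every row HDL plus printed LDL exceeds total cholesterol. The excess depends on TG only, so other choices of TC and HDL leave it unchanged.

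**Step 4, between-arm comparison.** Distortion of the raw mean LDL difference = 0.909 × mean TG difference: 0.1 gives 0.09, 0.3 gives 0.27 and 0.5 gives 0.45 mmol/L, with the sign of the TG difference.

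**Step 5, change from baseline.** If every visit uses the printed rule, each participant's change is distorted by 0.909 × the change in TG. If baseline comes from a laboratory value on the CRF and follow-up from the printed rule, the change carries a false rise of 0.909 × follow-up TG. On the TG range above, that is 0.73 to 2.73 mmol/L.

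**Step 6, IGT.** The 2-hour limits are identical. The fasting conditions, at least 7 and below 7 mmol/L, share no value, so nobody who meets one glucose rule can meet the other. Someone with fasting glucose below 7 and a 2-hour value from 7.8 to below 11 mmol/L meets the protocol's IGT rule but no glucose category in the SAP, because SAP IFG requires a 2-hour value below 7.8.

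**The case against.** Five points can be made for the plan.

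- **The relation is named and referenced, so the intention is recognisable.** This is so, but the SAP is what gets programmed, and a known intention is a reason to correct the line.
- **A laboratory LDL may be what is analysed.** Protocol 6.1.1 and the CRF source in SAP 1.8 allow this, and such a value would be unaffected. But SAP 1.17 says LDL is computed, and the documents do not reconcile the two. This limits the finding to LDL derived by the printed rule; it does not remove it.
- **The plus sign could be a text-conversion fault, or brackets around HDL + TG/2.2 could have been lost.** This cannot be excluded from the text alone. The minus before HDL in the same equation survived, so a lost sign is unlikely. The sponsor can check the source file and the code in minutes.
- **The internal argument proves only 0.455 × TG.** This is correct. The full 0.909 × TG is the excess over the minus-sign form. The step 4 shifts are exact for raw means and approximate for the covariate-adjusted robust estimate of SAP 1.9.
- **LDL is one of many secondary variables in a pilot, and the IGT point is narrow.** The primary analysis is indeed untouched. On IGT, the inclusion criterion in SAP Study population (FPG, OGTT or HbA1c) supports reading the two bullets as alternatives, and the IFG rule is the same in both documents. Screening is by HbA1c (protocol 4.1 and 6.2.1). The conflict then touches only participants who rely solely on the glucose-based IGT route, possibly few.

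**Conclusion.** The concern holds. As printed, SAP 1.17 gives LDL values above non-HDL cholesterol for every participant with TG above zero: at least 0.455 × TG too high on internal grounds, and 0.909 × TG above the minus-sign form. Under the assumed lipid values that is 0.73 to 2.73 mmol/L per participant. A TG difference between arms of 0.1 to 0.5 mmol/L would add a spurious LDL difference of 0.09 to 0.45 mmol/L. The result applies to LDL computed by the printed rule, in mmol/L, and not to a laboratory-reported value.

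The line must be corrected before analysis, because followed as written it makes a prespecified endpoint wrong. That rating rests on LDL alone.

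The IGT contradiction is real but lesser. It bears on the per-protocol exclusion and possibly on the IGR regression, and the number of participants affected cannot be computed from the documents. Neither point affects the primary ITT analysis of week-6 fasting glucose.

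**What to change.** - **SAP 1.17:** replace the plus sign before triglyceride/2.2 with a minus sign, and confirm that the analysis code agrees.
- **SAP 1.17:** add one sentence saying whether the analysed LDL is the calculated or the laboratory/CRF value, and use that source at baseline and at weeks 6, 12 and 26. Align the source given in the SAP 1.8 baseline table.
- **SAP Definitions:** reconcile the fasting-glucose condition for IGT with protocol 3.3, and state whether the HbA1c bullet is an alternative to the glucose bullet. This review takes no position on which threshold is right.

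The cost is one character and one sentence for LDL and one definition line for IGT. Data collection, sample size and design do not change.

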### **1.18 Variables related to clinical markers**

- Systolic and diastolic blood pressure (BP)
  - Derivation: the mean of two measurements of the blood pressure with a digital sphygmomanometer. Blood pressure will be measured after at least 5' rest.
  - Analysis: the analysis will be conducted separately for systolic and diastolic BP using modified ANCOVA and LMM as described above; no additional analysis.

### **1.19 Variables related to nutrition**

- Dietary intakes

- Derivation: dietary intakes (Total energy, carbohydrate, fat, saturated fat, salt and vitamin B6, B12, D) will be assessed using 24-hours recall questionnaire (food frequency questionnaire [FFQ]) at visits 4, 5, 7, 9 and 11. The FETA software will be used to derive average daily nutrition contents from the FFQ data. In addition, 25-hydroxyvitamin D and vitamin B6 will be measured directly by the Pathology Department in Hammersmith Hospital (Imperial College Healthcare NHS Trust).
- Analysis: the analysis will be conducted separately for each nutrient using modified ANCOVA and LMM as described above;
- Additional analysis: additional dietary intakes may be examined.

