Participants will then be reviewed after 6 and 12 weeks with repeat baseline measures. Participants in the control arm will be offered a personalised nutrition plan on completion of the study. Participants will be asked to complete a food frequency questionnaire (see Appendix 12) before their initial consultation with the dietitian (Visit 4 – see [Table 1](#)), and at the 6-, 12- and 26-week follow up clinical visits. Participants will also be asked to perform a 24-hour recall at each follow-up phone call with a dietitian (Visits 5, 7, 9 & 11 – see [Table 1](#)). A summary of the activities for each participant is given in [Table 1](#). Data from the App will also be used in exploratory analysis to examine usage patterns and decision making as a result of the DNA-based dietary recommendations.

See [Figure 1](#) for a diagram of the study design and estimated timeframe.

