12.2 TRIAL Suspension

In the event of the Imperial College Healthcare NHS Trust issuing a suspension of all non-essential clinical research activity, such as during the outbreak of COVID-19 in early 2020, all clinical visits to the ICRF will be suspended for the duration of the suspension. Phone-call visits will continue to be performed, as advised from the ICRF. For any participants for whom their clinical visits were to fall within the suspension period, their intervention period will be extended by the length of the suspension and their visits will re-commence once clinical research has resumed.

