### 1.7 Data description

Data will be collected as described in protocol version 0.18 of 16/07/2018 and managed as described in the data management system version 0.5 of 01/10/2018. Data will be collected in electronic case report form (eCRF) completed by investigators. All data will be on the virtual machine for the medical statistician to work with, the data will be in the form of data extractions (i.e. not the CRFs). If the original CRFs are needed, they will be provided in a read only format.

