## **Exploratory analyses**

The first pre-defined exploratory analysis will compare the exploratory arm with the two other arms. More specifically it will test the two following hypotheses: The exploratory arm confers similar or greater benefit compared to the interventional arm and greater benefit compared to the control arm.

The second hypothesis generating exploratory analysis will examine how the changes in leptin measurements correlate with changes in weight overall and by intervention arm. Leptin will be measured via saliva samples at weeks 0, 6, 12 and 26.

The last exploratory analysis will examine how outcomes in the exploratory arm vary across adherence levels. Adherence levels will be defined from the recorded activity of the application.

These analyses are exploratory in nature hence results will be interpreted cautiously.

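### SAP 1.19 treats the 24-hour recall and the FFQ as one instrument and lists only recall visits, leaving no follow-up FFQ, no week-6 intake and no exploratory-arm intake after Day 0

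*SAP*

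**What the plan says.** SAP 1.19 covers eight nutrients: energy, carbohydrate, fat, saturated fat, salt and vitamins B6, B12 and D. It says that they "will be assessed using 24-hours recall questionnaire (food frequency questionnaire [FFQ]) at visits 4, 5, 7, 9 and 11". The derivation follows: "The FETA software will be used to derive average daily nutrition contents from the FFQ data". Each nutrient is then analysed by modified ANCOVA and a linear mixed model.

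SAP 1.5 lists all eight under dietary intake and fixes the time points: "Secondary outcomes include differences at weeks 6, 12 and 26 between arms in the cross sectional values and changes from baseline". SAP 1.3 asks about the App's effect on the secondary outcomes, and the Exploratory analyses section states: "The first pre-defined exploratory analysis will compare the exploratory arm with the two other arms".

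The protocol keeps the two instruments apart. Under Protocol 3.4 the FFQ is completed before the first dietitian consultation (Visit 4) "and at the 6-, 12- and 26-week follow up clinical visits". Separately, participants are to "perform a 24-hour recall at each follow-up phone call with a dietitian (Visits 5, 7, 9 & 11". Protocol 6.2.2 adds a recall at Visit 4. Protocol 5, 6.2.2 and 6.2.3 limit the phone calls to the control and intervention arms.

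**The concern.** The SAP's wording points two ways. The instrument name and the visit list point to the recall. The FETA sentence and the time points in SAP 1.5 point to the FFQ. No single reading satisfies both, and the two readings use different data, different weeks and different arms. An analyst following the SAP would have to make an unplanned choice, in an open-label trial, for the endpoints that serve the first-listed secondary objective.

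Two further rules depend on that choice:

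- **Baseline.** The ANCOVA and change-from-baseline models in SAP 1.9 need a baseline value. Visit 4 could mean the Day 0 recall or the FFQ completed before it.
- **Imputation.** SAP 1.12 imputes missing data by MICE and makes no exception for measurements that were never scheduled. Read literally, it could impute follow-up recalls for an arm that receives no calls.

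**Working it through.** The plan gives no figure to reproduce here. The check sets the SAP's visit list against the protocol's schedule and then counts the planned data.

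**Inputs.** Visit days and arms come from Protocol 6.2.2 and 6.2.3. Arm sizes (60 each, 180 in total) come from Protocol 9.2.

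| Visit | Day | Instrument in protocol | Arms | In SAP 1.19 list |
|---|---|---|---|---|
| 4 | 0 | Recall (an FFQ is completed beforehand) | See note | Yes |
| 5 | 14 | Recall | Control, intervention | Yes |
| 6 | 42 | FFQ | All | No |
| 7 | 56 | Recall | Control, intervention | Yes |
| 8 | 84 | FFQ | All | No |
| 9 | 84 | Recall | Control, intervention | Yes |
| 10 | 182 | FFQ | All | No |
| 11 | 182 | Recall | Control, intervention | Yes |

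Note: Protocol 6.2.2 gives the Visit 4 recall to every participant, while the remark in Table 1 names only control and intervention.

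**Step 1: match the lists.** The SAP list {4, 5, 7, 9, 11} is identical to the protocol's recall visits. It shares none of the three follow-up FFQ visits {6, 8, 10}. SAP 1.15 itself maps weeks 6, 12 and 26 to Visits 6, 8 and 10, so the clash also exists within the SAP.

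**Step 2: can a visit window supply week 6?** Six working days span 8 to 10 calendar days. At the widest, Visit 5 ends by Day 14 + 10 = Day 24 and Visit 7 starts no earlier than Day 56 − 10 = Day 46. Neither reaches Day 42. SAP 1.13 allows ±3 days around Day 42, that is Days 39 to 45, which also misses both. The protocol's wider Visit 6 window could overlap an early Visit 7, but the SAP has no rule assigning that call to week 6.

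**Step 3: count the planned follow-up data for each intake.** The target is 180 participants × 3 time points = 540.

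| Reading | Week 6 | Week 12 | Week 26 | Total |
|---|---|---|---|---|
| SAP visits, read as FFQ | 0 | 0 | 0 | 0/540 |
| SAP visits, read as recall | 0/180 | 120/180 | 120/180 | 240/540 = 44.4% |
| Protocol FFQ schedule | 180/180 | 180/180 | 180/180 | 540/540 |

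Under the recall reading:

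- Control plus intervention have 240/(120 × 3) = 240/360 = 66.7%.
- The exploratory arm has 0/(60 × 3) = 0/180.

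Under the protocol's FFQ schedule the exploratory arm has 180/180.

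**The case against.** **Version drift.** SAP 1.7 states: "Data will be collected as described in protocol version 0.18 of 16/07/2018". The supplied protocol is later, since Protocol 12.2 refers to a suspension "such as during the outbreak of COVID-19 in early 2020". Other SAP details also differ from the supplied schedule, such as the ±3-day window at Visit 6 and anthropometry at Visit 4. The visit list may have been right for a schedule we cannot see. This stands as a possible explanation and limits the counts and the arm restriction to the supplied protocol. It does not remove the conflict inside the SAP between 1.19 on one side and 1.5 and 1.15 on the other.

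**The counts overstate the loss.** A sensible analyst would look for FFQ data where FFQs were done, so 0/540 describes the rule as written and not data that would be lost. The 44% includes the exploratory arm; for the main two-arm contrast the figure is 67%. The mixed model could also use the Day 14 and Day 56 recalls (120 + 120 planned). All of this is fair, but those recalls still give no week-6 value and nothing for the exploratory arm.

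**Limited scope.** SAP 1.19 also has vitamin B6 and 25-hydroxyvitamin D measured in the laboratory, so six of the eight nutrients (8 − 2) have no other source named there. All are secondary, and comparisons with the exploratory arm are exploratory. This stands and caps the severity.

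**Loose ends in the protocol.** The first FFQ is placed before Visit 4 in Protocol 3.4 and before Visit 3 in 6.2.1. Both are pre-intervention and compatible. The disagreement over an exploratory-arm recall on Day 0 is real, but it does not matter if recall analyses are confined to control versus intervention.

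**Conclusion.** The concern holds, with high confidence that SAP 1.19 contradicts the SAP's own time points. As written, the listed visits contain no follow-up FFQ visit, no week-6 visit and no exploratory-arm visit after Day 0. They yield 0/540 or 240/540 planned follow-up participant-timepoints, depending on the reading, against 540/540 under the protocol's FFQ schedule. These are planned numbers before dropout and rest on the supplied protocol's visits and arms.

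This is an error in a derivation rule, not a gap in data collection. It should be fixed before analysis, but it touches neither the primary endpoint nor the two laboratory vitamin measures.

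**What to change.** Amend SAP 1.19 as follows:

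- Derive the FETA intakes from the FFQ in all three arms, with the pre-intervention FFQ as baseline and Visits 6, 8 and 10 as weeks 6, 12 and 26.
- List the 24-hour recall (Visits 4, 5, 7, 9 and 11) as a separate instrument with its own Visit 4 baseline, supporting only control versus intervention after Day 0. If any intake endpoint is also wanted from the recalls, name it.
- State that recalls not scheduled for the exploratory arm are not missing data and are not imputed under SAP 1.12.

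In SAP 1.7, update the protocol version cited and check the visit list against it.

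The cost is SAP wording only. Data collection does not change, because the protocol already schedules the FFQ for every arm.
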